Abbreviation	Definition
A2C	apical 2-chamber
A3C	apical 3-chamber
A4C	apical 4-chamber
AE	adverse event
BMI	body mass index
CABG	coronary artery bypass graft
CAD	coronary artery disease
CFR	Code of Federal Regulations
CIOMS	Council for International Organizations of Medical Sciences
cm	centimeter
CMR	cardiac magnetic resonance
CRO	Contract Research Organization
DMC	Data Monitoring Committee
ECG	electrocardiogram
eCRF	electronic case report form
ED	effective dose
Echo	Echocardiogram
EEG	electroencephalography
EF	ejection fraction
FDA	Food and Drug Administration
GCP	Good Clinical Practice
GSM	Group sequential method
HEENT	head, ears, eyes, nose and throat
IB	Investigator's Brochure

Abbreviation	Definition
IC	informed consent
ICC	intra-class correlation coefficient
ICF	informed consent form
ICH	International Conference on Harmonization
IEC	Institutional Ethics Committee
IRB	Institutional Review Board
ITT	intent-to-treat
LC	liquid chromatography
LCX	left circumflex
LMI	Lantheus Medical Imaging
LV	left ventricular
LVEF	left ventricular ejection fraction
MedDRA	Medical Dictionary for Regulatory Activities
MI	myocardial infarction
mITT	modified intent-to-treat
MUGA	Multiple-gated acquisition
µg	microgram
mg	milligram
MI	mechanical index
min	minute
mL	milliliter
mmHg	millimeters of mercury
NCI-CTCAE	National Cancer Institute Common Terminology Criteria for Adverse Events
O ₂ Sat	oxygen saturation

Abbreviation	Definition
pH	potential of hydrogen
PFP	phospholipids-encapsulated perfluoropropane
PT	preferred term
QC	quality control
QT [interval]	interval on the ECG from the onset of the QRS complex to the end of the T-wave
QTcB	Bazett-Corrected QT interval
RCA	right coronary artery
RMSE	root mean square error
RR	respiratory rate
SAE	serious adverse event
SAF	Safety Evaluable Population
SAS®	Statistical Analysis System
sec	second(s)
SOC	system organ class
SP	safety population
TE	echo time
TEAE	treatment emergent adverse event
TIA	transient ischemic attack
TR	repetition time
US	United States
WOCBP	women of childbearing potential

1 INTRODUCTION

1.1 Background

Left ventricular (LV) volumes and ejection fraction (EF) are important clinical parameters for the diagnosis, management, and prognosis of subjects with cardiac diseases. Important treatment decisions and the evaluation of therapeutic effects are based on these parameters. Several techniques have been used for the analysis of LV volumes and EF, among them cine ventriculography, echocardiography, cardiac magnetic resonance (CMR) and computed tomography (Foley 2012).¹ CMR has evolved into the preferred reference technique because of its high spatial resolution and ability to obtain complete volumetric data sets, allowing very accurate determinations of regional and global LV function. Although the most frequently used modality in clinical practice, echocardiography has been hampered by its moderate reproducibility and accuracy to define LVEF. Poor acoustic windows and inadequate discrimination of the endocardial border are the main reasons for the poor reproducibility and accuracy of the test, besides geometric assumptions resulting from the two-dimensional approach (Foley 2012).¹ In a few studies, contrast echocardiography has been shown to allow improved assessment of LV volumes and EF, especially in subjects with difficult imaging conditions (Hoffman 2005, 2014.).^{2,3} Recent innovations in contrast-specific ultrasound techniques have further enabled improvements in visualization of the LV endocardial border above the level already shown in previous trials with the use of contrast-enhanced ultrasound imaging.

DEFINITY® (perflutren injectable suspension) is a sterile, non-pyrogenic suspension of phospholipids-encapsulated perfluoropropane microbubbles that is activated by shaking with the aid of the Vialmix™. In subjects with suboptimal echocardiograms, the addition of DEFINITY® improves the assessments of cardiac structure (ventricular chambers and endocardial borders) and function (regional wall motion).

The objective of this multicenter study is to determine the accuracy and inter-reader agreement of DEFINITY® contrast-enhanced and unenhanced 2D echocardiography for the assessment of LV volumes and EF in comparison with non-contrast CMR.

This trial will be conducted strictly according to the protocol, Good Clinical Practice (GCP), the sites' Independent Ethics Committees (IECs)/Institutional Review Boards (IRBs), and other related laws and regulations as applicable.

2 STUDY OBJECTIVES

2.1 Primary Objective

The primary objective of the study is to demonstrate improvement in accuracy in left ventricular ejection fraction (LVEF) assessment using DEFINITY® contrast-enhanced over unenhanced echocardiography.

2.2 Secondary Objectives

The secondary objectives of the study are to:

1. Demonstrate improvement in accuracy in left ventricular ejection fraction (LVEF) assessment using DEFINITY® contrast-enhanced over unenhanced echocardiography in subjects with suboptimal echocardiograms.
2. Demonstrate a reduction in inter-reader variability for the assessment of LVEF using DEFINITY® contrast-enhanced versus unenhanced echocardiography.
3. Demonstrate a reduction in inter-reader variability for the assessment of end-diastolic/systolic volumes using DEFINITY® contrast-enhanced versus unenhanced echocardiography.
4. Demonstrate a reduction in inter-reader variability for the assessment of LVEF using DEFINITY® contrast-enhanced versus unenhanced echocardiography in subjects with suboptimal echocardiograms.
5. Demonstrate a reduction in inter-reader variability for the assessment of end-diastolic/systolic volumes using DEFINITY® contrast-enhanced versus unenhanced echocardiography in subjects with suboptimal echocardiograms.

3 INVESTIGATIONAL PLAN

3.1 Overall Study Design and Plan

This is a Phase 3, prospective, open-label, multicenter study to evaluate LVEF measurement accuracy and reproducibility of DEFINITY® contrast-enhanced and unenhanced echocardiography as compared with non-contrast cardiac magnetic resonance imaging (CMR) used as the truth standard. Approximately one-hundred fifty (150) evaluable subjects will be enrolled and will undergo unenhanced and DEFINITY®-enhanced echocardiograms and CMR.

Subjects will be screened based on LVEF measurements obtained via 2D echo with or without contrast or other methods (e.g. CMR, MUGA scan) obtained within 6 months prior to enrollment. Subjects will be stratified to achieve an approximately even distribution within four pre-defined LVEF groups (>50, 41-50, 30-40, <30%) as measured by CMR. Subjects with optimal and suboptimal echocardiograms will be enrolled.

Each patient will undergo an unenhanced ultrasound examination and a DEFINITY® contrast-enhanced examination on the same day. A minimum of 360 seconds of images will be collected during both the unenhanced and the DEFINITY® contrast-enhanced examinations.

The site investigator will determine whether an echocardiogram is optimal or sub-optimal based on the unenhanced echocardiogram performed on Day 0. An echocardiogram is considered suboptimal if 2 or more segments of the ventricular border are classified as not adequately visualized in any one of the 3 apical views.

Subjects will remain at the clinical site for at least 30 minutes of observation after the end of the administration of DEFINITY®. A safety follow-up telephone call will be conducted for all subjects at approximately 72 ± 24 hours after completion of the imaging sessions.

Enrolled subjects will be followed for AEs, SAEs, and changes in concomitant medications from the time the Informed Consent is signed through the safety follow-up telephone call.

[figure not shown]
Unenhanced and DEFINITY®-enhanced echocardiograms will be performed with standard apical 2 chamber, apical 3 chamber, and apical 4 chamber, (A2C, A3C, and A4C, respectively) views. DEFINITY®-enhanced echocardiograms will be performed using low or very low mechanical index (MI) imaging. Images will be recorded in standard digital format, masked to patient identifiers, and sent to a central echocardiography facility for analysis. There, 3 experienced independent blinded readers will interpret the results according to the Image Review Charter; additional analyses will also be performed as described in the Image Review Charter. Each reader's independent interpretation will be recorded in a database.

CMR images will also be collected and independently read at a central laboratory by a single reader.

The schedule of events is provided in Appendix 1.

Figure 3-1 displays an overview of study events.

Figure 3-1 **Study Event Overview**

3.2 Rationale for Study Design

The study is intended to demonstrate the utility of DEFINITY® contrast-enhanced echocardiography in providing accurate and reproducible measurements of LVEF and LV volumes as compared with unenhanced 2D echocardiography using non-contrast CMR as the truth standard.

A broad-based population with known or suspected cardiac disease with either optimal or suboptimal 2D echocardiograms or other imaging methods from which LVEF can be derived (e.g. CMR, MUGA scan) will be included.

The primary endpoint of improved accuracy in LVEF measurement will be assessed from the results of an independent assessment and subsequent analysis conducted by the central imaging laboratory. Secondary endpoints will also be assessed, including accuracy in the suboptimal echocardiogram subset and inter-reader variability in the overall population and the suboptimal echocardiogram subset.

Interpretation of images will be conducted with a blinded read by three experienced physicians at a central imaging laboratory who are not associated with patient recruitment. In addition, a single, independent, blinded echocardiologist will read each subject's unenhanced echocardiogram as either optimal or suboptimal. This will be independent of the site investigator determination performed at Day 0. The independent readers will employ a prospectively defined and standardized methodology described in the Image Review Charter, which will reduce the potential for variation in the criteria used for image reads.

CMR images will also be collected and read independently at a central imaging laboratory, using a methodology that will also be described in the Image Review Charter.

3.3 Study Duration

All screening assessments will occur within 7 days prior to enrollment/DEFINITY® administration (Day 0). Non-contrast CMR studies will occur within \pm 30 days of DEFINITY® administration. Safety monitoring will begin with the signing of the informed consent and continue up to 72 \pm 24 hours post-DEFINITY® administration. The expected duration of subject participation is not more than 41 days. Subjects are expected to be enrolled over a 10 month period.

4 STUDY POPULATION

Approximately one hundred and fifty (150) evaluable subjects who have previously undergone a 2D echocardiogram with or without contrast or other assessment (CMR, MUGA scan) will be enrolled in this trial. The study population will consist of male and female subjects 18 years of age or older.

Enrollment will be stratified according to CMR LVEF to achieve an approximately even distribution across four subgroups (LVEF >50, 41-50, 30-40, <30%). LVEF for screening purposes will be determined by the investigator and based on measurements with 2D echo or other methods (e.g. CMR, MUGA scan) obtained within 6 months prior to enrollment (Day 0). Subjects with optimal and sub-optimal echocardiograms will be enrolled. Suboptimal echocardiograms will be based on the site investigator's evaluation of the unenhanced echocardiography images obtained on Day 0. An echocardiogram is considered suboptimal if 2 or more segments of the ventricular border are classified as not adequately visualized in any one of the 3 apical views.

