5.5 Blinding

This is an open-label study; therefore, no blinding procedures are required for investigators and subjects.

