6.8 Echocardiography Imaging Procedures

6.8.1 Image Acquisition

A bedside resting transthoracic echocardiogram will be performed by personnel trained in study procedures according to standardized instructions provided here and in the study Imaging Manual. Unenhanced echocardiography will be performed in each of the standard A2C, A3C, and A4C views after optimization of these views. At least 3 consecutive cardiac cycles should be recorded in standard digital format in each view. After unenhanced imaging has been conducted, study drug will be administered as described above and in the Dose Preparation and Administration Guide. DEFINITY®-enhanced images will be obtained with low or very low MI imaging using a standardized and harmonized method consistent with practice guidelines. After study drug administration and subsequent image optimization, the same A2C, A3C, and A4C views should be obtained as with unenhanced imaging over at least 3 consecutive cardiac cycles.

Subjects will remain at the site for observation until at least 30 minutes after the end of the administration of study drug.

All images will then be transferred to an Imaging Core Laboratory for further analysis. No site analysis will be performed. Instructions for echo data transfer and storage at the central imaging laboratory will be provided in the study Imaging Manual.

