8.2. Secondary Efficacy Endpoint(s) and Analyses

8.2.1. Improvement in accuracy in LVEF assessment using DEFINITY® contrast-enhanced over unenhanced echocardiography in subjects with suboptimal echocardiograms

The primary endpoint analysis will be repeated in the subset of subjects with suboptimal echocardiograms. This will include all primary analyses described in sections 8.1 and 8.1.1, excluding the supportive analyses at the end of section 8.1. The study is not powered to reject the primary endpoint null hypothesis, so the focus is more on the estimate of $\mu_D - \mu_U$, on Bland-Altman plots and on the Deming regression for each blinded reader. There will be no imputation of missing LVEF data for this analysis.

8.2.2. Reduction in inter-reader variability for the assessment of LVEF using DEFINITY® contrast-enhanced versus unenhanced echocardiography

The inter-reader variability among each pair of readers within each imaging modality will be estimated using an intra-class correlation (ICC) and its two-sided 95% CI. The ICC assesses rating reliability by comparing the variability of different ratings of the same subject with the total variation across all ratings and all subjects. The inter-observer variability in the assessment of LVEF between two readers will be determined by percentage of error. The percentage of error will be calculated using the following formula:

$$\text{Percentage of error} = (\text{SD between 2 measurements} / \text{mean of the 2 measurements}) \times 100$$

The mean percentage of error and its 95% CI will be calculated for each pair of readers within each imaging modality. The pairwise ICCs and percentages of error differences will be compared descriptively between contrast-enhanced and unenhanced echocardiography.

In addition, specific to only section 8.2.2, there will also be a separate ICC analysis to assess intra-reader variability as approximately 10% of all echo results will be re-read by each reader.

This document is confidential.

8.2.3. Reduction in inter-reader variability for the assessment of end-diastolic/systolic volumes using DEFINITY® contrast-enhanced versus unenhanced echocardiography

The same analysis used to assess inter-reader variability on LVEF (section 8.2.2) will be conducted for end-diastolic/systolic volumes.

8.2.4. Reduction in inter-reader variability for the assessment of LVEF using DEFINITY® contrast-enhanced versus unenhanced echocardiography in subjects with suboptimal echocardiograms

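### Two optimal/suboptimal calls are collected, the analysis sections do not say which forms the suboptimal subset, and the only defining text points to an unblinded site call with no timing rule

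*Protocol*

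**What the plan says.** **Site call.** Protocol section 4 and SAP section 3.4 base suboptimal status on the site investigator's "evaluation of the unenhanced echocardiography images obtained on Day 0". The protocol synopsis, protocol 3.1 and SAP 3.3 also assign this determination to the site investigator. The criterion in protocol section 4 is: "An echocardiogram is considered suboptimal if 2 or more segments of the ventricular border are classified as not adequately visualized", in any one of the three apical views.

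**Central call.** The protocol synopsis, protocol 3.2 and SAP 3.3 add a single independent blinded echocardiologist, who reads each subject's "unenhanced echocardiogram as either optimal or suboptimal". Protocol 3.2 adds: "This will be independent of the site investigator determination performed at Day 0".

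**Day 0 conduct.** Protocol 6.8.1 orders the imaging: "After unenhanced imaging has been conducted, study drug will be administered as described above", after which the same views are repeated. It also says: "No site analysis will be performed". Under protocol 5.5, "no blinding procedures are required for investigators and subjects".

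**Analysis.** SAP 8.2.1 says: "The primary endpoint analysis will be repeated in the subset of subjects with suboptimal echocardiograms". SAP 8.2.4 and 8.2.5, and protocol 8.3.1.1, 8.3.1.4 and 8.3.1.5, refer to the same subgroup. None of them says whose classification is used.

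**The concern.** A subset analysis of a contrast agent is interpretable only if membership is fixed by something that the contrast images cannot influence. The blinded central read of the unenhanced images meets that condition. The site call is not protected in the same way. The investigator may see the enhanced images in the same session, and whether a segment is adequately visualized is a judgement. A border seen clearly with contrast could change the view of a borderline unenhanced segment.

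Three of the five secondary endpoints are at stake: LVEF accuracy, inter-reader variability of LVEF, and inter-reader variability of volumes, each in suboptimal echocardiograms. SAP 8.2.1 says the subset is not powered for the test and puts the emphasis on the estimated difference in mean absolute error. Selection would distort exactly that quantity. Leaving the source unnamed also allows it to be chosen after both classifications are known.

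**Working it through.** **1. Which call forms the subset?** The analysis sections (protocol 8.3.1.1, 8.3.1.4, 8.3.1.5; SAP 8.2.1, 8.2.4, 8.2.5) do not say. The only sentence in either document stating what suboptimal status rests on is in protocol section 4 and SAP 3.4, and it names the site. The central read is described but assigned to no analysis.

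**2. Is the site call fixed before contrast?** Protocol 6.8.1 orders the acquisitions but not the classification. The Day 0 list in SAP 3.8.2 and the schedules in protocol Appendix 1 and SAP 13.1 contain no step for it. It is placed on Day 0 and nothing more.

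**3. The plan's own figure.** Protocol 8.2.1 gives 90% power with 150 enrolled, a difference of 2.75 and an SD of 10. Protocol 8.6 gives about 143 evaluable. The noncentrality is 2.75 × √143 / 10 = 3.29. With the two-sided 0.05 critical value of 1.97681 (142 df), power is 90.4%, so the figure reproduces. No figure is given for the subset. If 30%, 50% or 70% of 143 are suboptimal (43, 72 or 100 subjects; an assumption), power for the same difference is 42%, 63% or 78%. The standard error, 10/√n, is 1.5, 1.2 or 1.0 points.

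**4. Sensitivity A: no true benefit.** Assume the per-subject gain (unenhanced minus enhanced absolute error) has mean 0 and SD 10, and that the call has correlation r with that gain. A share p is labelled suboptimal. The spurious subset gain is r × 10 × φ(z)/p, where z is the upper-p normal quantile.
- p = 50%, r = 0.1: 0.1 × 10 × 0.399/0.5 = 0.8 points; r = 0.2: 1.6 points.
- p = 30%, r = 0.1: 0.1 × 10 × 0.348/0.3 = 1.2 points; r = 0.2: 2.3 points.

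The chance per reader of a significant result favouring DEFINITY, nominally 2.5%, becomes 10% to 11% at r = 0.1 and 27% to 32% at r = 0.2. A negative r gives the mirror image against DEFINITY. The documents give no value for r.

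**5. Sensitivity B: real overall gain of about 2 points.** Simulation with 1,000,000 subjects. All settings are assumptions:
- Unenhanced visibility vU and enhanced visibility vD are correlated 0.3.
- Raw error SDs are 10·exp(−k·vU) and 7.5·exp(−k·vD).
- The half of subjects with the lowest vU − w·vD + noise (SD 0.5) is called suboptimal.

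Positive w means that good contrast images push the call towards suboptimal. Negative w means that poor ones do.

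| k | Subset gain, w = 0 | w = 0.25 to 1.0 | w = −0.25 to −1.0 |
|---|---|---|---|
| 0.15 | 2.7 | 2.8 to 2.9 | 2.5 to 2.2 |
| 0.25 | 3.2 | 3.4 to 3.6 | 2.9 to 2.4 |
| 0.35 | 3.7 | 4.0 to 4.4 | 3.4 to 2.6 |

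With positive w, 7% to 27% of subjects change label. The upward shift is 0.1 to 0.6 points and the downward shift 0.1 to 1.2. The standard error of the subset mean at 72 subjects is about 1.0 to 1.2 points under these settings.

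**6. Inter-reader endpoints.** No calculation was made for endpoints 4 and 5; the same argument about selection applies by reasoning only.

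**The case against.** A reader might infer that the subset is settled as the site call, that the call is made after contrast, that the bias favours DEFINITY, and that protocol 6.8.1 contradicts the call altogether. The documents do not support any of these.

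- **Settled definition.** The defining sentence stands in the population sections. The analysis sections name no source, and the blinded central read covers every subject. If that read forms the subset and its reader sees only the unenhanced study, this bias cannot arise.
- **Late call.** The criterion uses unenhanced images only, and unenhanced imaging is finished before drug is given, so a call at that point is quite possible. Absence of a timing rule is not evidence of a late call.
- **Direction.** Site staff are given no core-laboratory LVEF or CMR reading, so influence could come only through visual impression. A good contrast study might prompt a suboptimal label, or a poor one might reinforce the idea of a difficult patient. The two move the estimate in opposite directions.
- **Contradiction.** The sentence on site analysis sits between image transfer and data-transfer instructions and recurs for CMR in 6.7.1. It reads naturally as no site measurement.

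The consequence is also limited: the subset is unpowered, the inter-reader comparisons are descriptive, and in Sensitivity B the upward shifts are below one standard error. What remains is that the protected classification has no assigned use, while the only defining text points to the unprotected one. A shift smaller than the standard error is still systematic and does not appear in the confidence interval.

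**Conclusion.** The concern holds in this form: the source of the suboptimal subset is unspecified where it matters, the only defining text points to an unblinded call with no timing rule, and a blinded alternative already planned is not put to use. The subset estimates for secondary endpoints 1, 4 and 5 could therefore depend on the contrast images.

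The documents determine neither the size nor the direction. The shifts in the working depend on the assumed subset share, strength of influence and sign, and they show only that a modest influence could matter to an estimate of a few ejection-fraction points. The primary endpoint is unaffected because it uses all eligible mITT subjects regardless of this classification. The change is worth making because it removes an avoidable source of bias at almost no cost.

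**What to change.** - In protocol 8.3.1 and SAP 8.2.1, 8.2.4 and 8.2.5, state that the blinded central read of the unenhanced images defines the suboptimal subset, and that its reader does not see the enhanced images. Repeat the analyses with the site call as a sensitivity analysis, and report agreement between the two calls (for example, kappa).
- Align protocol section 4 and SAP 3.4 with this. SAP 3.3 omits the per-view condition that SAP 3.4 contains; use one criterion throughout.
- If the site call is kept as the definition, require it to be recorded, time-stamped and locked before the DEFINITY images are viewed. Do not fill late or missing site calls from the central read, because that would mix two classifiers in one subset.
- Reword the site-analysis sentence in protocol 6.8.1 so that it exempts the Day 0 image-quality call.

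The cost is a few sentences and one extra set of subset tables. The central read is already planned, and the sample size does not change. Keeping the site call would add one time field and a short recording step at the site.
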